9.2.5 Subject observation and discontinuation after investigational product (IP) administration

The IP administration guidelines in **Appendix 1** list the study requirements for subject observation and discharge after IP administration.

9.3 Definition of an Adverse Event

An Adverse Event (AE) is any untoward medical occurrence in a subject or clinical investigation subject temporally associated with the use of a medicinal product, whether or not considered related to the medicinal product. The occurrence does not necessarily have to have a causal relationship to the treatment received in the study. An AE can therefore be any unfavorable and unintended sign (including an abnormal laboratory finding, for example), symptom, or disease (new or exacerbated) temporally associated

with the use of a medicinal product, whether or not considered related to the medicinal product.

Examples of an AE include:

- Exacerbation of a chronic or intermittent pre-existing condition including either an increase in frequency or intensity of the condition.
- Significant or unexpected worsening or exacerbation of the condition/indication under study.
- A new condition detected or diagnosed after study therapy administration even though it may have been present prior to the start of the study.
- Pre- or post-treatment events that occur as a result of protocol-mandated procedures (e.g., invasive protocol-defined procedures, modification of a subject's previous treatment regimen).

An AE does **not** include:

- Medical or surgical procedures (e.g., colonoscopy, biopsy). The medical condition that leads to the procedure is an AE.
- Social or convenience hospital admissions where an untoward medical occurrence did not occur.
- Day to day fluctuations of pre-existing disease or conditions present or detected at the start of the study that do not worsen.
- The disease/disorder being studied or expected progression, signs, or symptoms of the disease/disorder being studied unless more severe than expected for the subject's condition.

9.4 Definition of Adverse Reaction

An adverse reaction is any adverse event caused by a drug. Adverse reactions are a subset of all suspected adverse reactions, for which there is reason to conclude that the drug caused the event.

9.5 Definition of Suspected Adverse Reaction

Suspected adverse reaction means any adverse event for which there is a reasonable possibility that the drug caused the adverse event. For the purposes of IND safety reporting, 'reasonable possibility' means there is evidence to suggest a causal relationship between the drug and the adverse event. A suspected adverse reaction

implies a lesser degree of certainty about causality than adverse reaction, which means any adverse event caused by a drug.

9.6 Definition of Serious

An adverse event (AE) or suspected adverse reaction is considered “serious” if it:

1. results in death
2. is life-threatening (at risk of death at the time of the event)
3. requires inpatient hospitalization or prolongation of existing hospitalization

NOTE: Complications that occur during hospitalization are AEs. If a complication prolongs hospitalization or fulfills any other serious criteria, the event is serious. Hospitalization for elective treatment of a pre-existing condition that did not worsen from baseline is not considered to be an AE.

4. Results in disability/incapacity

NOTE: The term disability means a substantial disruption of a person’s ability to conduct normal life functions. This definition is not intended to include experiences of relatively minor medical significance such as uncomplicated headache, nausea, vomiting, diarrhea, influenza, accidental trauma (i.e., sprained ankle) that may interfere or prevent everyday life functions but do not constitute a substantial disruption.

5. Is a congenital anomaly/birth defect.

Important medical events that may not result in death, be life-threatening, or require hospitalization may be considered an SAE when, based upon appropriate medical judgment, they may jeopardize the subject and may require medical or surgical intervention to prevent one of the outcomes listed in the above definition.

9.7 Definition of Unexpected

An adverse event or suspected adverse reaction is considered “unexpected” if it is not listed in the investigator brochure, protocol, ICF, or is not listed at the specificity or severity that has been observed; or, if an investigator brochure is not required or available, is not consistent with the risk information described in the general investigational plan or elsewhere in the current application.

9.8 Clinical Laboratory Assessments and Other Abnormal Assessments as Adverse Events and Serious Adverse Events

Abnormal laboratory findings (e.g. clinical chemistry, hematology) or other abnormal assessments (e.g., vital signs) that are judged by the Investigator as clinically significant will be recorded as AEs or SAEs if they meet the definition of an AE as defined in Section 9.3 (“Definition of an Adverse Event”) or SAE, as defined in Section 9.6 (“Definition of a Serious Adverse Event”) and will assess intensity based on the criteria defined in Section

9.10. Clinically significant abnormal laboratory findings or other abnormal assessments that are detected during the study or are present at screening and significantly worsen following the start of the study will be reported as AEs or SAEs. However, clinically significant abnormal laboratory findings or other abnormal assessments that are associated with the disease being studied, unless judged by the Investigator as more severe than expected for the subject's condition, or that are present or detected at the start of the study but do not worsen, will not be reported as AEs or SAEs.

The Investigator will use the normal laboratory ranges (or a change in baseline in subject's whose laboratory tests were outside of the normal range when enrolled), as well as the NIH CTCAEv5 when exercising medical judgment in assessing whether abnormal laboratory values are clinically significant.

9.9 Recording of Adverse Events and Serious Adverse Events

The Investigator should review all documentation (e.g., hospital progress notes, laboratory, or diagnostic reports) relative to the event being reported. The Investigator will then record all relevant information regarding an AE/SAE into the electronic data system. It is not acceptable for the Investigator to send photocopies of the subjects' medical records in lieu of completion of the appropriate AE/SAE pages.

The Investigator will attempt to establish a diagnosis of the event based on signs, symptoms, and/or other clinical information. In such cases, the diagnosis should be documented as the AE/SAE and not the individual signs and symptoms.

SAEs will be reported to the IRB within 10 working days or within 24 hours if the event is life-threatening or results in death.

Pregnancies

Subject pregnancy must be reported to the Principal Investigator within 24 hours of awareness of the event. Any subject that becomes pregnant during the study must be promptly withdrawn from the study. Follow-up information regarding the outcome of the pregnancy and any postnatal sequelae in the infant will be required.

9.10 Intensity of Adverse Events and Serious Adverse Events

The Investigator will make an assessment of intensity for each AE and SAE reported during the study. The assessment will be based on the Investigator's clinical judgment and CTCAEv5.

An AE that is assessed as severe should not be confused with an SAE. Severity is a category utilized for rating the intensity of an event; and both AEs and SAEs can be assessed as severe. An event is described as 'serious' when it meets one of the pre-defined outcomes as described in Section 9.6, "Definition of Serious."

9.11 Causality of Adverse Events and Serious Adverse Events

The Investigator is obligated to assess the causality between study therapy and the occurrence of each AE/SAE. The Investigator will use clinical judgment to determine if there is a reasonable possibility that the biological action of the study therapy was responsible for AE/SAE being reported. Alternative causes such as natural history of the underlying diseases, concomitant therapy, other risk factors, and the temporal relationship of the event to the study therapy will be considered and investigated. The Investigator will also consult the Clinical Investigator's Brochure and/or Product Information, for marketed products, in the determination of his/her assessment.

The Investigator will use the following questions when assessing causality of an adverse event to study therapy.

Is there a reasonable possibility that the study therapy caused the event? Reasonable possibility implies that there is evidence that the event was caused by the study product. An affirmative answer designates the event as a suspected adverse reaction.

There may be situations when an SAE has occurred and the Investigator has minimal information to include in the initial report. However, it is very important that the Investigator always makes an assessment of causality.

The relationship between AEs and the study exposure will be classified by the investigator as:

| | |
|-----------|---|
| None: | No relationship. Related to other known etiologies, conditions, or exposures. |
| Unlikely: | Current knowledge suggests that a relationship is unlikely. |
| Possible: | A plausible temporal sequence or response pattern exists but the AE may be related to other known etiologies, conditions, or exposures. |
| Probable: | A plausible temporal sequence or response pattern exists and the AE cannot be related other known etiologies, conditions, or exposures. |
| Definite: | A plausible temporal sequence or response pattern exists and the AE can be confirmed by re-challenge or with other supporting data |

9.12 Follow-Up of Adverse Events and Serious Adverse Events

After the initial AE/SAE report, the Investigator is required to proactively follow each subject and provide further information on the subject's condition. All AEs and SAEs documented at a previous visit/contact that are designated as ongoing will be reviewed at subsequent visits/contacts.

Adverse events and SAEs will be followed until resolution, until no further changes in the event are expected (i.e. the point at which a subject experiencing a critical adverse event is treated successfully and stabilized even though they may continue to experience lingering sequelae that may never resolve), until the subject is lost to follow-up, or until it is agreed that further follow-up of the event is not warranted (e.g. non-serious, study therapy unrelated, mild or moderate adverse events ongoing at a subject's final study visit). If a subject dies during participation in the study or during a recognized follow-up period, the Investigator will provide a copy of any post-mortem findings, including histopathology.

New or updated information will be recorded by modifying the AE forms in the electronic data system

9.13 Timeframes for Submitting SAE Reports

Once an Investigator becomes aware that an SAE has occurred in a study subject, he/she will record the information in the electronic data record within 48 hours. Any fatal or life-threatening event must be reported within 24 hours. If the Investigator does not have all information regarding an SAE, he/she will not wait to receive additional information before recording the event in the data system and completing as much information known at the time of the submission. The reporting timeframes for any SAE occurring during the study are summarized in Table 2.

TABLE 2
Serious Adverse Event Reporting Requirements

| Type of SAE | Initial Reports | | Follow-Up Reports |
|----------------------|--|--------------------------|-------------------|
| | Fatal or Life-Threatening | Other SAEs | Any SAE |
| Reporting Timeframes | 24 hours | 48 hours | 48 hours |
| Documents Required | 24 hours: Complete as much information in the electronic data system that is known. 48 hours: Fully complete all AE forms | Fully completed AE forms | Updated AE Forms |

9.14 Post-Study Adverse Events and Serious Adverse Events

The Investigator should report any death or SAE occurring at any time after a subject has completed or terminated a clinical trial, when such death or SAE may reasonably be related to the study therapy used in an investigational trial. Investigators are not obligated to actively seek AEs from former study participants.

9.15 Regulatory Aspects of Adverse Event Reporting

The Investigator will promptly report all SAEs within the timeframes specified in Section 8.13. Prompt notification of SAEs by the Investigator is essential so that UMMSM can meet legal obligations and fulfill ethical responsibilities towards the safety of all subjects participating in UMMSM-sponsored investigational trials.

The Investigator will comply with the applicable local regulatory requirements related to reporting of SAEs to his or her Institutional Review Board (IRB) or Independent Ethics Committee (IEC).

This protocol has been filed under an Investigational New Drug (IND) application with the FDA. A given SAE may qualify as an Expedited Safety Report (ESR) if the SAE is both at least possibly attributable to study therapy and unexpected. In this case, all Investigators participating in an IND study will receive an ESR.

The ESRs are prepared according to UMMSM policy and are forwarded to the Investigator as necessary. The purpose of the ESR is to fulfill specific regulatory and Good Clinical Practice (GCP) requirements regarding the product under investigation. Based on previous trials involving intravenous infusion of allogeneic human MSCs, no AEs have been attributed to treatment administration; therefore, all AEs will be considered and documented as unexpected AEs.

All AEs occurring at any time during the trial will be collected, documented, and reported by the investigator. For each AE, the investigator will provide the date of onset and resolution, intensity, treatment required, outcome, seriousness, and potential causality with regards to the study exposure.

10. STATISTICAL ANALYSIS

10.1 Determination of Sample Size and Analysis Population

No formal statistical justification was performed to determine sample size in this Phase I/II study. The allocation ratio will be 1:1. All randomized subjects will be included in summaries of baseline characteristics, safety, and efficacy. Reasons for study discontinuation will be tabulated.

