2.2.2. Secondary Endpoints

Efficacy:

- Cardiac catheterization angiography, CFR and FFR measurement to assess post-coronary angiography coronary artery endothelial function at 6 months post-infusion
- Target lesion lumen loss by QCA at 6 months post-infusion
- Endothelialization and stent site vessel healing parameters by OCT (only applicable if participant undergoes PCI).
- Circulating angiogenic and inflammatory markers at 1-, 3-, and 6-months post-infusion.
- Seattle Angina Questionnaire (SAQ) Angina Frequency and Quality of Life scales at 1-, 3-, and 6-months post-infusion.

Safety:

- Incidence (at one (1) month post-infusion) of any treatment-emergent serious adverse events (TE-SAEs), defined as the composite of: death, non-fatal MI, stroke, hospitalization for heart failure, sustained ventricular arrhythmias (characterized by ventricular arrhythmias lasting longer than 30 sec or with hemodynamic compromise) or atrial fibrillation.

- Incidence of Major Adverse Cardiac Events (MACE), defined as the composite incidence of (1) death, (2) hospitalization for cardiovascular events, or (3) non-fatal MI at 12 months.
- Treatment emergent adverse event (AE) and serious adverse event (SAE) rates through the duration of the study.
- Target Vessel Failure (revascularization, death, or MI attributed to the target vessel) post-PCI (only applicable if participant undergoes PCI).
- Abnormal hematology and clinical chemistry value results.

Exploratory:

- Detailed molecular and functional assessment (genomic, proteomic, proliferation, senescence and differentiation, and angiogenic assays) of bone marrow aspirate at 3 months post-infusion.

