6.7 Study Investigational Therapy Management

6.7.1 Investigational Product Labeling and Storage

The product label contains the elements required by the CFR and other national and local authorities for investigational products. ISCI GMP Cell Processing Facility will directly store and deliver the designated cell processing technologist in the CPL, and will be kept cryopreserved in liquid nitrogen vapor phase until shortly before administration. Investigational product must be stored in a securely locked enclosure. Access is strictly

limited to unblinded CPL personnel prior to preparation for infusion. After preparation for infusion, the Investigator and his or her designees are permitted to administer the Investigational Product only to subjects participating in this protocol.

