2. A physical examination will be performed and may include the following examinations: general appearance; skin and nails; limbs; head, eyes, ears, nose, throat (HEENT) and neck; respiratory; cardiovascular; and abdominal. Vital Signs measurements will consist of: height, weight, heart rate, blood pressure, respiratory rate, oxygen saturation, and temperature. Height is only required at screening. If physical exam and vitals were performed as “Standard of Care” within 7 days of signing ICF, those results may be extracted from patient medical records and used for the screening visit in this study. The screening visit physical exam can be completed by the participants’ treating physician.
3. Concomitant medications will be recorded at screening visit and updated at each visit.
4. Randomization can be performed within 7 days prior to IP infusion.
5. Refer to Appendix 1 for Infusion guidelines.
6. Refer to hospital protocols for coronary angiogram guidelines. Results from the screening cardiac catheterization may be extracted from patient medical records and used for the purposes of this study. Subjects who did not have a stent placed at screening will not undergo the coronary angiogram (and associated measurements) at Month 6, but should complete the other assessment listed on Time and Events Table, per investigator’s judgement.
7. Subjects who did not have a stent placed at screening may still undergo the coronary angiogram (and associated measurements) at Month 6, but should complete the other assessment listed on Time and Events Table. All procedures (CFR, FFR, IFR, IVUS, and/or OCT) will be performed in accordance with the established hospital protocols which are done as “Standard of Care”. Subjects who undergo PCI at screening should have CFR, FFR, IFR, IVUS, and/or OCT measurements if available, as per investigator’s judgement.
8. Refer to Appendix 2 for Brachial Ultrasound (Brachial Artery Ultrasound to assess endothelial function must be performed prior to 12pm).
9. Bone Marrow Biopsy will be performed at month 3 visit. Separate ICF will be used for this optional sub-cohort. The bone marrow biopsy can be performed in the Catheterization Laboratory or in Interventional Radiology department, either with or without imaging guidance (X-Ray or Ultrasound).
10. All subjects will be asked to complete the Seattle Angina Questionnaire (SAQ), EQ-5D, and SF-36 quality of life questionnaires. Only male subjects will be asked to

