complete the IIEF questionnaire, and only female subjects will be asked to complete the SQOL-F questionnaire.

11. Subjects must be fasting for at least 8 hours prior to blood collection as required by standard of care. If labs were performed as “Standard of Care” within 7 days of signing ICF, those results may be extracted from patient medical records and used for the screening visit in this study. The minimal laboratory requirements include:

Hematology Tests:

Complete Blood Count with Differential (WBC, RBC, hemoglobin, hematocrit, MCV, and platelets; Diff: neutrophils, lymphocytes, monocytes, eosinophils, and basophils).

Chemistry Tests: (fasting required)

Comprehensive Metabolic Panel (glucose, sodium, potassium, chloride, bicarbonate, blood urea nitrogen, creatinine, total protein, albumin, alkaline phosphatase, total bilirubin [fractionate if total >1.5 times normal], alanine transaminase (ALT), aspartate transaminase (AST), and GFR).

Coagulation Tests: Prothrombin time (PT/INR), activated partial thromboplastin time (aPTT).

Urinalysis: Routine Urinalysis with reflex to culture.

Glycosylated Hemoglobin: HbA1c

Biomarkers: SST: (2 Gold or Tiger top serum separator tubes) Transcriptomic/proteome (RNA, mRNA, protein samples, and telomerase, akt); growth factors (sdf-1, notch); functional assays (cell-growth rate, VEGF, and CFU assays), PRA, and more.

Immune monitoring: MNCs: (2 Green top sodium heparin tubes) CD3*CD25* or CD3*CD69* and more.

Gene Expression: peripheral blood will be collected prior to infusion on Day 0, and at the 6 month follow up visit to analyze DNA & RNA (DNA to be collected at one time point only).

EPC-CFU Assay: Blood samples (5 Lavender top tubes) to measure Endothelial Progenitor Cell-Colony Forming Units (EPC-CFU).

Viral Serology: Infectious disease tests – HIV, HIV 2, Hep B (HBsAg), Hep C (Anti-HCV), and CMV.

Serum Pregnancy Test: Serum β HCG test will be completed at screening and within 36 hours prior to infusion in women of childbearing potential only.

If subjects are unable to come to the site for specified visits alternative methods for assessments (e.g., phone contact, virtual visit, alternative location for assessments, including local labs or imaging centers) could be implemented when necessary.

8 Study Phases and Visits

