8.2 Baseline and Day 0 Visit

See Table 1 for the procedures and assessment to be performed during the baseline visit of the study. This visit will occur after all screening tests are completed and it has been determined that the subject meets eligibility criteria. This visit should occur within 0 - 30 days post-coronary angiogram.

See Table 1 for the procedures and assessment to be performed during the Day 0 visit of the study. The Day 0 visit will occur within 0 - 30 days post-coronary angiogram after all baseline tests are completed and it has been determined that the subject remains eligible. Once the subject is deemed eligible to continue in the study, the subject will be administered the investigational product. Refer to Appendix 1 for Infusion Guidelines.

8.3 Week 2, Month 1, Month 3, Month 6, and Month 12 (Post-Infusion Visit)

See Table 1 for the procedures and assessment to be performed for the Week 2, Month 1, Month 3, Month 6, and Month 12 study visits. Subjects who had a stent placed at screening will have a follow up coronary angiography at 6 months post-investigational product infusion to evaluate the treated lesion lumen loss with quantitative coronary angiography (QCA), physiology with fractional flow reserve (FFR) and endothelial function with coronary flow reserve (CFR). Outpatient visits should be completed as close to the scheduled visit dates as possible. There will be a window of ± 5 days for week 2 and ± 2 weeks for the Month 1, 3, 6, and 12 study visits.

An optional sub-study will be conducted on at least 5 participants from each treatment group in which they will undergo a bone marrow biopsy at Month 3 for a detailed molecular (genomic, proteomic, proliferation, senescence and differentiation assays) and functional assessment (angiogenic assays) of the effect of allogeneic MSCs on bone marrow derived autologous MSC and EPCs. All subjects will be asked to sign a separate ICF before participating in this optional sub-study. Due to the blinded nature of the study, more than 10 subjects will be enrolled in this sub-study and Cell Manufacturing lab will inform the clinical team once 5 subjects from each treatment complete the bone marrow biopsy. In the interest of participant safety, the bone marrow biopsy may be performed under ultrasound guidance (X-Ray or Ultrasound) by interventional radiology department, if indicated by investigator's clinical judgement.

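### Safety is summarised on all randomised subjects, so anyone randomised but never infused would dilute the treatment-emergent, post-infusion event rates

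*Combined protocol and SAP*

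**What the plan says.** Section 10.1 sets one population for every purpose: "All randomized subjects will be included in summaries of baseline characteristics, safety, and efficacy". Neither 10.1 nor 10.2 defines a treated or safety set, and 10.1 does not say whether safety is grouped by assigned or by received product.

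Table 1 in Section 7 places randomisation at the Baseline visit and infusion at Day 0. Item 4 of the table key adds: "Randomization can be performed within 7 days prior to IP infusion". Section 8.2 puts Day 0 "after all baseline tests are completed and it has been determined that the subject remains eligible", and makes the infusion conditional: "Once the subject is deemed eligible to continue in the study, the subject will be administered the investigational product". Two further checks come close to the infusion:

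- The serum pregnancy test "will be completed at screening and within 36 hours prior to infusion in women of childbearing potential only" (Section 7, table key item 11).
- Section 9.2.1 sets a resting oxygen-saturation threshold to be met before infusion.

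Section 4.4 lets subjects withdraw at any time and allows some withdrawals to be replaced.

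Two safety endpoints in Section 2.2.2 depend on exposure. One is the incidence of treatment-emergent serious adverse events (TE-SAEs) one month after infusion. The other is "Treatment emergent adverse event (AE) and serious adverse event (SAE) rates through the duration of the study". Section 9.2.4 also has the DSMB follow the proportion with a TE-SAE in the 30 days after administration, without naming a denominator.

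**The concern.** A treatment-emergent event presupposes treatment. A subject who was randomised but never infused has no infusion date from which to count one month or 30 days, and cannot have an event that emerged on treatment. Under 10.1 as written, that subject still counts in the denominator.

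The error runs one way. It lowers the apparent rate, and it also lowers the upper confidence limit, because the interval is computed as if more people had been exposed than were. In an arm of 15, one such subject is 6.7% of the denominator. Section 11.2 describes the study as designed to test safety, and the DSMB reviews safety data by group. The treatment-emergent rates are therefore a main product of the trial, and their denominator should be the people exposed.

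**Working it through.** **Can a subject be randomised and not infused?** Setting the sections side by side:

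1. Randomisation is a Baseline procedure and may come up to 7 days before infusion (Table 1; key item 4).
2. Infusion follows only once the subject is found still to be eligible (8.2).
3. The repeat pregnancy test may fall up to 36 hours before infusion, and the saturation check belongs to the infusion visit (Section 7, key item 11; 9.2.1). Both can come after randomisation.
4. Withdrawal is possible at any time (4.4).

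So the design leaves such a route open, and no text removes these subjects from the safety summaries.

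**Inputs.** From the documents: 15 subjects per arm (3.1) and two-sided 95% intervals (10.2). Assumed: k = 0 to 3 never-infused subjects in an arm, x = 0 to 3 events, and exact (Clopper-Pearson) limits, since the plan names no interval method. The plan gives no event rate, dropout figure or sample-size justification, so it has no figure of its own to reproduce.

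**Rates.** The reported rate is x/15 and the rate among the exposed is x/(15 − k). Their ratio is (15 − k)/15, so the relative understatement is k/15 whatever the value of x: 6.7%, 13.3% or 20.0% for k = 1, 2 or 3.

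**Zero events.** The upper limit is 1 − 0.025^(1/n). For n = 15 this is 1 − 0.025^(1/15) = 21.8%; for n = 13 it is 1 − 0.025^(1/13) = 24.7%.

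| Not infused (k) | Infused (n) | Zero-event upper limit: all 15 / infused | Two events: all 15 / infused |
|---|---|---|---|
| 0 | 15 | 21.8% / 21.8% | 13.3% / 13.3% |
| 1 | 14 | 21.8% / 23.2% | 13.3% / 14.3% |
| 2 | 13 | 21.8% / 24.7% | 13.3% / 15.4% |
| 3 | 12 | 21.8% / 26.5% | 13.3% / 16.7% |

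For two events and k = 2, the 95% interval is 1.7% to 40.5% on 15 subjects and 1.9% to 45.4% on 13. At the ends of the range considered, one event with k = 1 reads 6.7% instead of 7.1%, and three events with k = 3 reads 20.0% instead of 25.0%.

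**If never-infused subjects are replaced.** With 15 infused out of 15 + k randomised, the understatement is k/(15 + k) = 6.2%, 11.8% or 16.7% for k = 1, 2 or 3. The zero-event upper limit would be reported as 20.6%, 19.5% or 18.5% instead of 21.8%.

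**How likely is at least one?** If each of 30 subjects independently has probability p of not being infused, the chance is 1 − (1 − p)^30. For p = 2%, 5% and 10% (assumed) this gives 45%, 79% and 96%.

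**The case against.** The strongest reply is that the effect is conditional and small. The documents forecast no uninfused subjects. Item 4 of the table key permits a gap of up to 7 days but does not require one, and 8.2 does not say whether the eligibility decision comes before or after randomisation. Even with two of 15 not infused, the two-event rate moves by 2.1 points inside an interval running from 1.7% to 40.5%. Some visibility is also protected: 10.1 tabulates reasons for discontinuation, and the DSMB event tables in 11.8 show each subject's date of treatment. All of this stands, and it limits the size of the point. It does not supply the missing definition. The late pregnancy and saturation checks and withdrawal leave a route to non-infusion however 8.2 is read.

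Three stronger readings are tempting, and the documents do not support them.

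- **That every safety endpoint is affected.** In 2.2.2, major adverse cardiac events are counted at 12 months, target vessel failure is counted after PCI, and abnormal laboratory values carry no label. None of these is called treatment-emergent, and a never-infused subject could have any of them.
- **That the plan assigns safety events to the randomised arm even when the other product was given.** Section 10.1 says only who is included; on grouping it is silent.
- **That randomisation should move to Day 0.** The product "will be kept cryopreserved in liquid nitrogen vapor phase until shortly before administration", which might suggest that no lead time is needed. But 6.1 requires CMV matching and attention to penicillin allergy, and preparation follows a manual that is not among the documents. Whether the lead is needed cannot be judged from the text, and the denominator problem is solved without moving it.

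One further objection shapes the fix. Adverse events are reviewed from Baseline (Table 1), and events before treatment that result from protocol-mandated procedures count as adverse events (9.3). A safety set limited to infused subjects would drop such events in the uninfused unless they are reported elsewhere.

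**Conclusion.** The point holds for the treatment-emergent, post-infusion rates: TE-SAE incidence at one month, treatment-emergent AE and SAE rates, and the 30-day proportion in 9.2.4 if it takes its denominator from 10.1. For these, the rule as written counts unexposed subjects and understates both the rate and its upper limit.

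The missing definition is certain from the text; the dilution is not. It needs at least one randomised subject who is not infused, and the documents give no number. Without replacement, the relative understatement equals that subject's share of the arm, 6.7% for each of 15. In absolute terms it is about 0.5 to 5 percentage points over one to three events and one to three uninfused subjects. This is small against the imprecision of 15 per arm, but its direction is always favourable to the product. If every randomised subject is infused, no figure changes.

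**What to change.** Amend Section 10.1 to say three things:

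1. Baseline and efficacy summaries include all randomised subjects, by assigned arm.
2. The safety set, used for treatment-emergent rates and for the 30-day TE-SAE proportion in 9.2.4, is all subjects in whom an infusion was started, grouped by product received.
3. Adverse events in subjects randomised but not infused are listed separately, so that none is lost.

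Section 9.2.4 should refer to this set as its denominator. The change should be in place before safety is first summarised by arm.

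The cost is a few lines of text. No new data are needed, and randomisation timing and subject care are unaffected. The one downside for the sponsor is that the stated safety rates and upper limits may become slightly less favourable.
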